8.4 Baseline

Enrollment/Baseline Visit (Visit 1, Week 1)

Pre-intervention assessments will be conducted by [name], [name], [name] or an MCRI research assistant. These assessments will take place at MCRI. Participants may find the assessment sessions to be tiring and small breaks should be provided when needed. The assessments will comprise the following tasks and are estimated to take 2 – 2.5 hours to complete:

1. Stanford Sleepiness Scale – The SSS is a single item self-report assessment of current levels of sleepiness. Children are asked to rate their current level of sleepiness on a 7 point scale ranging from 1 (very awake) to 7 (very sleepy). This measure is expected to take no more than 5 minutes to complete.
2. Test of Everyday Attention for Children (Tea-Ch2) will be used to assess attention. Children aged 4 to 7 will complete 4 subscales from junior version which are either facilitated by or wholly completed on the computer. The subtests are designed to assess selective attention (Balloon Hunt; Balloons 5) and sustained attention (Simple Reaction Time; Sustained Attention to Response Task). Children aged 8 to 9 years will complete 4 equivalent subscales from the older version (Hector Cancellation; Hector-B; Simple RT and SART). The battery should take no more than 20 minutes to complete. This measure provides both raw score and scaled scores for each of the subtests.
3. Child Attention Network Task (ANT) – a child friendly version of the flanker task which is suitable for children aged 4 years and above. The Anticipated Response task - a stop signal task that measures the ability to rapidly prevent already initiated actions. The Child ANT would enable assessment of interference control and the Anticipated Response task assessment of response inhibition, both aspects of attentional control. These measures are administered on a laptop and should take no more than 30 minutes in total to complete.
4. Corsi Block-Tapping Test (forwards and backwards) – Visuospatial working memory. Children are required to replicate a sequence by clicking the corresponding blocks on the screen. This test is administered on a laptop and should take no more than 10 minutes to complete. This measure provides a raw score of the number of sequences children have correctly replicated.

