9 OUTCOMES

9.1 Primary outcome

The primary outcome is an improvement in cognitive attention, as measured by the Test of Everyday Attention for Children (selective and sustained attention) and experimental paradigms of attentional control (interference control with the Child ANT test and response inhibition with the anticipated response task) between the intervention and control group at post-training.

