13 STATISTICAL METHODS

13.1 Sample Size Estimation

A priori power analysis using G*Power 3.1 estimated a required sample between 40 (for a large effect size) and 98 (for a medium effect size) participants based on the following parameters:

- ANOVA: repeated measures between factors
- estimated effect size f .4 (large) and .25 (medium)
- alpha .05
- power .8
- Number of groups: 2
- Number of measurements: 2
- Correlation among measures: .5

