13.2 Statistical Analysis Plan

Primary outcome – Cognitive attention: selective attention, sustained attention, response inhibition, and interference control

- Mean scores for selective and sustained attention, response inhibition and interference control for the intervention and control groups, across each time point will be presented.
- Latent Growth Curve Modelling will be used to analyse the difference in scores both within and between the intervention and control group, across all four time points.

Secondary outcomes – (include) behavioural attention, working memory, social skills, and mathematic ability

- Mean scores for each variable, for each group, across each time point will be presented.
- Latent Growth Curve Modelling will be used to analyse the difference in scores on the above variables both within and between groups, across all four time points.

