13.2.3 Methods of analysis

Primary outcome measure

To meet the primary objective of the study, the four primary outcome measures: response inhibition, interference control, selective attention, and sustained attention as measured by the Anticipated Response task, Child ANT, and TEA-Ch 2 respectively, will be analysed using Latent Growth Curve Modelling (LGCM) using a multigroup approach. An alpha level of .05 and two-tailed tests will be used for this analysis. LGCM will be conducted through R. Participants will be compared to their own baseline at each of the three subsequent testing time points, and further comparisons will be made between time points (e.g. 5 week follow up and 3 month follow up, 5 week follow up and 6 month follow up). Participants in the TALI program group and the active contact group will also be compared at each time point. LGCM will allow for baseline ability to be taken into consideration.

Secondary outcomes measures

To meet the secondary objective of determining whether improvements in cognitive attention transfer to improvements in other domains including mathematics ability, working memory and social functioning in children with ABI who complete the TALI attentional training program, further LGCM will be used as described above with the secondary outcome variables listed in section 9.2.

Additional analysis

To meet the secondary objective of identifying factors which predict improvement in attention in children with ABI who complete the TALI attentional training program, LGCM will be used. Predictor variables will be obtained through data collected from the demographic screening survey including age at time of injury, type of injury, length of time since injury, severity of attentional deficits and socio-economic background, as well as from data obtained through assessment measures relating to motivation, sleep, mental health and family functioning.

To meet the final secondary objective of investigating whether there are differences in the types of attentional deficits found in typically developing children, when compared with children with ABI, children's scores on the Connor's EC/3 will be compared using an independent samples, two-tailed ANOVA with an alpha level of .05

Data on typically developing children will be obtained from previous study database, whereby participants consented to their de-identified data being used for further research.

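### Four primary measures are each tested at an unsplit two-sided .05 with no success rule, and the primary analysis is not confined to the post-training contrast that defines the outcome

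*Protocol*

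**What the plan says.** Section 13.2.3 of the protocol names "the four primary outcome measures: response inhibition, interference control, selective attention, and sustained attention" and sets the level for them in one sentence: "An alpha level of .05 and two-tailed tests will be used for this analysis".

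The same paragraph then lists the comparisons that serve the primary objective:
- within participants: "Participants will be compared to their own baseline at each of the three subsequent testing time points", followed by comparisons of one follow-up with another;
- between arms: "Participants in the TALI program group and the active contact group will also be compared at each time point".

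Section 13.2, under its primary-outcome heading, has the same breadth (the number at the end of the quote counts the assessments): "Latent Growth Curve Modelling will be used to analyse the difference in scores both within and between the intervention and control group, across all four".

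The outcome definition is narrower. Section 9.1 lists the same four constructs and places the contrast "between the intervention and control group at post-training". The synopsis does likewise, and Section 3.1 frames the objective as a comparison with children who do a control task.

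Section 13.1 sizes the trial for one test at alpha .05.

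**The concern.** The trial is meant to support one conclusion, that the programme improves attention in children with ABI. The protocol offers four measures on which to base it, gives each the full 5% level, and does not say whether one, some or all must be significant. A reader therefore cannot tell what error rate attaches to that conclusion. It is not 5% unless a rule is added.

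The definition and the analysis also differ in scope. Section 9.1 points to one contrast at one visit. Sections 13.2 and 13.2.3 spread the primary analysis over all visits and include change within each arm. If a late difference or a within-arm gain were reported as the primary finding, nothing in Section 13 would rule it out. Within-arm gains are a particular hazard. Sections 8.4 to 8.6 give the same attention tasks at every visit, so practice or maturation can raise scores in both arms without any effect of the programme.

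**Working it through.** **Inputs.** Alpha .05, two-sided, and four measures (13.2.3). Three post-baseline visits (8.5, 8.6). Two groups, two measurements, correlation .5 among repeated measures, f = .40 or .25, power .8 (13.1). Planned N = 80 (5.1). The correlation between different measures is not in the protocol. It is an assumption, varied here from 0 to .8.

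**1. The protocol's own sample size.** For a repeated-measures ANOVA, between factors, the noncentrality is λ = f²·N·m / (1 + (m − 1)ρ), with 1 and N − 2 degrees of freedom.
- f = .40, N = 40: λ = .16 × 40 × 2 / 1.5 = 8.53, power 81.2%.
- f = .25, N = 98: λ = .0625 × 98 × 2 / 1.5 = 8.17, power 80.8%.

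Both stated figures (40 and 98) are reproduced, with one test at .05 and no allowance for four.

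**2. Four between-arm tests at post-training, no true effect.** Under independence the chance of at least one significant result is 1 − .95⁴ = 18.5%. In the direction favouring TALI it is 1 − .975⁴ = 9.6%. For correlated measures, treat the four test statistics as equicorrelated normal variables:

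| Correlation between measures | Either direction | Favouring TALI |
|---|---|---|
| 0 | 18.5% | 9.6% |
| .3 | 17.4% | 8.7% |
| .5 | 15.6% | 7.8% |
| .8 | 11.4% | 5.7% |

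A single test gives 5% and 2.5%.

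**3. Four measures at three post-baseline visits, if any visit may count.** Under independence, 1 − .95¹² = 46.0% in either direction and 1 − .975¹² = 26.2% favouring TALI. Repeated scores on one child are not independent. Taking the protocol's .5 as the correlation over time, simulation from a multivariate normal gives:

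| Correlation between measures | Either direction | Favouring TALI |
|---|---|---|
| 0 | 41.5% | 23% |
| .3 | 39% | 20% |
| .5 | 35.6% | 18% |

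The same simulation with a between-measure correlation of .8 gives about 27% and 13%.

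**4. Power under a split level, N = 80, same model as step 1.** For f = .25, λ = .0625 × 80 × 2 / 1.5 = 6.67. Power is 72.2% at .05 and 51.3% at .05/4 = .0125. For f = .40 it is 98.3% and 93.9%. The total N for 80% power at .0125 rises from 40 to 56 (f = .40) and from 98 to 138 (f = .25).

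**The case against.** The best defence is that the primary contrast is already named. The synopsis and Section 9.1 restrict it to intervention against control at post-training, and Section 3.1 defines the objective as a comparison with control. On that reading the family is four tests, not twelve, and within-arm change is not the efficacy criterion. This is right as far as it goes, and it is why 16-19% is the main figure. It does not settle the matter. Sections 13.2 and 13.2.3 do not carry the restriction into the primary analysis, and four tests at full alpha still exceed 5%.

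It can also be said that a separate analysis plan may deal with multiplicity. But Section 13.2 is itself titled as the statistical analysis plan, and it fixes both the level and the list of comparisons. The point concerns what it fixes.

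Some stronger readings are tempting and are not supported:
- **A useless programme has up to a 46% chance of a result in its favour.** That figure counts differences in either direction and needs twelve independent tests. In TALI's favour the independence ceiling is 26%.
- **The plan lets any one of twelve tests prove efficacy.** The protocol states no success rule at all, so it does not state this one. The twelve-test figures are conditional on such a use.
- **Section 13.2.3 turns one outcome into four.** Section 9.1 already lists all four constructs. The inconsistency lies in visits and contrasts, not in the number of measures.
- **There are really six primary scores.** Section 8.4 lists two TEA-Ch2 subtests for each of two constructs, but nothing says they are tested separately.
- **Within-arm tests add to the false-positive rate for efficacy.** They answer a different question. The remedy is to bar them as evidence of efficacy, not to count them.

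**Conclusion.** The point holds. As written, the trial's main conclusion has no 5% error control. Even the mildest case computed (four tests, one visit, measures correlated at .8) gives 11.4%, more than twice the nominal level. The plausible figure at post-training is about 16-19%. The 36-42% range applies only if a difference at any follow-up visit is accepted; it rests on the protocol's .5 correlation over time and on assumed correlations of 0 to .5 between measures. Chances of a false result in TALI's favour are about half of these: 6-10% and 18-23%, against 2.5% for one test. Sections 13.2 and 13.2.3 need to be reconciled with Section 9.1 whatever correlation is assumed.

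**What to change.** In Section 13.2.3, replace the alpha sentence with wording to this effect:

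*The confirmatory test for each of the four measures is the between-arm difference at post-training, as defined in Section 9.1. The four p-values are adjusted by Holm to a familywise two-sided .05, and efficacy is claimed only for measures significant after adjustment. Comparisons at 3 and 6 months, and all within-arm comparisons, are supportive and carry no efficacy claim.*

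Bring the primary-outcome bullets of Section 13.2 into line. No change in data collection is needed.

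The cost is lower power per measure at the first Holm step: from about 72% to 51% for f = .25 at N = 80, and from 98% to 94% for f = .40. Later Holm steps use larger levels (.05/3, .05/2, .05), so the loss shrinks once one measure has succeeded. These powers come from the protocol's own ANOVA model, not from the growth-curve analysis.

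Two alternatives also hold the error at 5% or less without splitting alpha. Naming one primary measure in advance keeps the 72% but demotes the other three. Requiring all four to succeed is far more demanding: with 72.2% power each and independent measures, the chance of all four is .722⁴ = 27%, and higher if they are positively correlated. Whichever is chosen, it should be written in before the allocation is revealed.

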5.2.1 Inclusion criteria

Participants must meet all of the following criteria to be enrolled in this study:

- Is between the ages of 4 years and 9 years 11 months at the time of randomisation.
- Has a primary diagnosis of an ABI.
- Has an attentional deficit as determined by the Conners EC/3 parent rating scale. Children who score above 60 (t-score: elevated range) on either of the subscales relating to inattentive behaviour (inattention: DSM Inattentive) of the Conners 3, or on the inattention/hyperactivity subscale of the Conners EC will be deemed eligible for inclusion in the trial.
- At least 6 months has passed since the time of injury, or in the case of ABI due to cancers, since the conclusion of treatment (including chemotherapy).
- Has a legally acceptable representative capable of understanding the informed consent document and providing consent on the participant's behalf.

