5. Digit Span task (forwards and backwards) – Auditory working memory. Children are required to replicate a sequence of digits by selecting them from a circle of digits on the screen. This task is administered on a laptop and should take no more than 5 minutes to complete. This measure provides a raw score of the number of accurately recalled digits.
6. Paediatric Evaluation of Emotions, Relationships and Sociability (PEERS) – Measures social skills. This is a game-based computerised task which is administered via a touchscreen tablet. Children will be asked to complete the Emotion Perception and Emotion Recognition subtests from the Social Cognition Domain, and the Non-verbal Gestures and Social Perception subtests from the Social Communication Domain. These domains were selected as there are the areas of social functioning thought to be most impacted in children with Acquired Brain Injuries. This task should take no more than 10 minutes to complete.
7. The Wechsler Individual Achievement Test II (WIAT II) is a standardised measure of mathematics ability. The WIAT II can be used with both children and adults. Children will complete the numerical operations and mathematical reasoning subtests to give a measure of mathematics ability. Starting points are based on the child's age and children progress until they make six consecutive errors. Completion time is expected to take no more than 30 minutes.
8. Intrinsic Motivation Scale – This is a child-specific 18 item self-report measure of motivation with regards to school and schoolwork. This measure provides a score relating to the child's overall motivation. This task should take no more than 10 minutes to complete.

Parents will be asked to complete the following, note the time to complete all measures is estimated at less than 2 hours:

1. Strengths and Weaknesses of ADHD symptoms and normal behaviour – The SWAN is an 18 item parent report questionnaire based on DSM-5 criteria for ADHD. The SWAN provides raw scores on children inattentive, and impulsive/hyperactive behaviours. Higher scores on this measure indicate greater attention difficulties.
2. Children’s Sleep Habits Questionnaire – The CSHQ is a 33 item parent report sleep screening assessment tool. The CSHQ provides a total score and 8 subscale scores, assessing key domains of sleep, both medical and behavioural. Higher scores across subscales indicate greater sleep concerns.

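### Age at randomisation is not named as a covariate in the arm comparisons, although the children span six years and several outcomes are raw or carry no described age norm

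*Protocol*

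**What the plan says.** Section 13.2.3 of the Protocol analyses the four primary outcomes (selective attention, sustained attention, interference control, response inhibition) by multigroup LGCM. It compares the arms at each time point and adds "LGCM will allow for baseline ability to be taken into consideration". For the secondary outcomes, "further LGCM will be used as described above with the secondary outcome variables listed in section 9.2". No other covariate is named for these models. Age at injury and time since injury appear only in the separate analysis of what predicts improvement.

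On age, section 5.2.1 admits a child who "Is between the ages of 4 years and 9 years 11 months at the time of randomisation". Section 7 stratifies by injury severity in three strata and not by age.

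On score type, section 8.4 says of the Corsi test: "This measure provides a raw score of the number of sequences children have correctly replicated". Of the digit span it says: "This measure provides a raw score of the number of accurately recalled digits". The SWAN is also raw, but is a parent rating. The TEA-Ch2 yields raw and scaled scores, and the one to be analysed is not named; children of 4 to 7 and of 8 to 9 take different forms. The WIAT-II is called standardised. No score type or age norm is described for the Child ANT or the Anticipated Response task, which supply two of the four primary measures.

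**The concern.** Performance on attention and memory tasks can be expected to change between 4 and 10 years of age, and the protocol itself picks test forms by age. Where a score is not age-normed, differences in age between children add to the variance of an arm comparison unless the model removes them. The baseline score removes part of this, but one measurement with error does not remove all of it.

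Age is needed for eligibility, so it is known for every child, and treatment cannot affect it. Precision matters here: section 13.1 puts the requirement for a medium effect at 98 children, while section 5.1 plans 80.

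**Working it through.** **Inputs from the protocol.** N = 80, 40 per group (5.1); allocation 1:1 (7); two-sided alpha .05 (13.2.3); f = .25 or .4, power .8, two measurements, between-visit correlation r = .5 (13.1). With two equal groups d = 2f, so f = .25 is d = .5.

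**Assumed.** The age-score correlation a is not in the protocol. It is taken as equal at both visits and varied from .3 to .6. A second value, r = .7, is a sensitivity assumption.

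**Step 1: the plan's own figures.** For the between-factor test in a repeated-measures ANOVA, noncentrality = f² × N × m / (1 + (m − 1) × r), with 1 and N − 2 degrees of freedom.
- f = .4, N = 40: .16 × 40 × 2 / 1.5 = 8.53, power 81.2%.
- f = .25, N = 98: .0625 × 98 × 2 / 1.5 = 8.17, power 80.8%.

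Both stated sizes reproduce. At N = 80 and f = .25 the noncentrality is 6.67 and power is 72.2%.

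**Step 2: baseline-adjusted contrast without age.** Residual variance is 1 − r² = .75. The squared noncentrality is .5² / (.75 × 4/80) = .25 / .0375 = 6.67, again 72.2% power. This is the reference.

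**Step 3: add age.** R² = (r² + a² − 2ra²) / (1 − a²), and residual variance is 1 − R². For r = .5 and a = .5: R² = (.25 + .25 − .25) / .75 = .333, so the residual is .667, a cut of 1 − .667/.75 = 11%. Equivalent N is 80 × (residual without age) / (residual with age). Power is from the noncentral t at d = .5.

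| r | a | Residual, baseline | Residual, baseline + age | Cut | Equivalent N | Power before | Power after |
|---|---|---|---|---|---|---|---|
| .5 | .3 | .750 | .725 | 3% | 82.7 | 72.2% | 73.6% |
| .5 | .4 | .750 | .702 | 6% | 85.4 | 72.2% | 75.0% |
| .5 | .5 | .750 | .667 | 11% | 90.0 | 72.2% | 77.2% |
| .5 | .6 | .750 | .609 | 19% | 98.5 | 72.2% | 80.7% |
| .7 | .3 | .510 | .501 | 2% | 81.4 | 87.1% | 87.7% |
| .7 | .4 | .510 | .493 | 3% | 82.8 | 87.1% | 88.2% |
| .7 | .5 | .510 | .480 | 6% | 85.0 | 87.1% | 89.0% |
| .7 | .6 | .510 | .459 | 10% | 88.8 | 87.1% | 90.3% |

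**Step 4: the growth-model slope.** Step 3 describes a contrast at one visit. For a linear growth model with visits at 0, 6, 13 and 26 weeks (assumed variances: intercept .5, slope .1, residual .5), the variance of the slope difference with age was divided by that without age, for an age effect that is stable over the six months.
- Group intercepts free: ratio 1.00 at a = .3, .5 and .6. The intercept factor absorbs age.
- Baseline intercepts held equal: .97, .89 and .81 at a = .3, .5 and .6.

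**Step 5: outer bound.** A comparison at one visit with no baseline adjustment would gain a², that is 9% to 36%. This applies only if the arm comparisons at each time point are run without baseline.

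**The case against.** The strongest objection is that the plan is silent rather than wrong. A reader might infer that it adjusts for baseline alone and rules age out. The text supports neither: it contains no closed covariate list, the stratification factor is not named either, and a separate analysis plan, not available here, may list more. This stands against calling the omission an error. It weighs less against the recommendation, because section 13.2 is itself headed as the statistical analysis plan, already fixes model, alpha and software, and names one adjustment.

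A reader might also infer that raw, heavily age-dependent scores affect every primary and secondary contrast. The protocol gives no figure for age dependence. The two task scores it states to be raw are secondary outcomes. TEA-Ch2 covers two of the four primary measures and also yields scaled scores; if those are age-normed, which the protocol does not say, most of the gain on them goes. The WIAT-II is described as standardised.

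The gain in Step 3 belongs to a single-visit contrast, and Step 4 shows that it can vanish for the slope. That stands. However, section 9.1 places the primary comparison at post-training and section 13.2.3 compares the arms at each time point, so the single-visit contrast is relevant.

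The upper end of the range also needs care. The between-visit correlation within age is (r − a²) / (1 − a²): .33 at a = .5 and .22 at a = .6 when r = .5. An age correlation of .7 would give a 32% cut, but it implies a within-age correlation of .02, so that figure should not be relied on. If age drives scores strongly, r is probably above .5 and the gain is smaller.

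Finally, a chance difference in age between arms under randomisation is not bias. The issue is precision.

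**Conclusion.** The point holds as a recommendation on efficiency. Baseline ability is the only adjustment named, age at randomisation is not named, and the age span, the stratification and the score types make age the natural further covariate.

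At r = .5, N = 80 and d = .5, the gain for a baseline-adjusted contrast is 3% to 19% of residual variance, or about 1.4 to 8.5 points of power, for an assumed age correlation of .3 to .6. At r = .7 it is 2% to 10%. For a slope difference with free group intercepts and a stable age effect it is about nil. The benefit therefore lies mainly in the arm comparisons at post-training and at the other visits, on outcomes without age norms. The missing statement of the TEA-Ch2 score type decides whether two of the four primary measures are among them.

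**What to change.** In section 13.2.3, before unblinding:

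- For every outcome analysed as a raw or otherwise not age-normed score, prespecify age at randomisation (in months, centred at the mean of both arms together) as a covariate on the intercept and on each growth factor.
- Constrain the age effects to be equal in the two arms. A multigroup model otherwise estimates them separately in each arm.
- Include age in the arm contrasts at post-training and at the other time points, and keep the baseline score.
- State whether TEA-Ch2 raw or scaled scores are analysed. If raw, say how scores from the two age-specific forms are put on one scale.

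The cost is a few sentences and, with the equality constraint, one parameter per growth factor. No new data are needed. Fixing the covariate in advance also avoids a choice made after seeing whether the arms differ in age.
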